### 8.4. Study size

The study will aim to enroll 1000 PLWH with VL <50 copies/mL, without present or past evidence of viral resistance to, and no prior virological failure with agents of the NNRTI and INI class initiating CAB+RPV LA regimen.

There is no formal statistical hypothesis to be tested in these analyses. The study will focus on absolute effectiveness estimation. Confidence intervals, constructed using the exact Clopper-Pearson method based on the cumulative probabilities of the binomial distribution, are presented in Table 2, 3, 4 and are designed to give estimates of precision.

It is anticipated that data from 1000 participants are thought adequate to meet the study objectives. In the ATLAS study in which participants switched from their PI, NNRTI, or INSTI based oral triple therapy regimen to CAB+RPV LA regimen, the percentage of participants with virologic failure (2 confirmed HIV RNA  $\geq$ 50 copies/mL) and treatment discontinuation were, respectively, 1.6% (95% CI 0.5 to 3.4) and 8.4% (95% CI 5.6 to 12.1) at week 48. Among the 3 individuals with confirmed virological failure, all selected drug resistance mutations. For resistance, we assume a 50% resistance rate at month-24 among those with virological failure.

With 1000 individuals, the precision for the estimation of virologic failure rate will range between 0.9 and 1.5% for a failure rate ranging from 2 to 6% as shown below in Table 2.

Confidence Level	Sample Size (N)	CI Width	Virologic Failure (P)	Lower Limit	Upper Limit
0.95	1000	0.019	0.02	0.012	0.031
0.95	1000	0.023	0.03	0.020	0.043
0.95	1000	0.025	0.04	0.029	0.054
0.95	1000	0.028	0.05	0.037	0.065
0.95	1000	0.031	0.06	0.046	0.077

The corresponding precision for the discontinuation rate will range between 1.7 to 2.3 for a rate ranging from 8 to 16% as shown below in Table 3.

Confidence Level	Sample Size (N)	CI Width	Discontinuation (P)	Lower Limit	Upper Limit
0.95	1000	0.035	0.08	0.064	0.099
0.95	1000	0.038	0.10	0.082	0.120
0.95	1000	0.041	0.12	0.101	0.142
0.95	1000	0.044	0.14	0.119	0.163
0.95	1000	0.046	0.16	0.138	0.184

If the virological failure rate is ranging from 2 to 6%, then the number of participants to be tested for genotypic resistance will range from 20 to 60 individuals. With these numbers of subjects, the precision for the estimation of resistance rate will range from 12.7% (with 60 individuals) to 21.9% (with 20 individuals) for resistance rate of 50%, as shown below in table 4.

Confidence Level	Sample Size (N)	CI Width	Resistance (P)	Lower Limit	Upper Limit
0.95	20	0.46	0.5	0.27	0.73

0.95	30	0.38	0.5	0.31	0.69
0.95	40	0.32	0.5	0.34	0.66
0.95	50	0.28	0.5	0.36	0.64
0.95	60	0.26	0.5	0.37	0.63

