# AIM 3. Assess the clinical effectiveness among PLWH who initiate CAB+RPV LA regimen

Given that this study involves PLWH in routine clinical care, and who may not attend clinic appointments at 6, 12 or 24 months, a window of 12 weeks around the date in question will be used for virologic failure. Thus, the proportion with virologic failure during first six months, at 6, 12 or 24 months  $\pm$  6 weeks will be used; and if none is available, the first measurement during first six months, after 6, 12 or 24 months (and at most 6 weeks after the measurement).

Proportion of participants who continue to be suppressed (VL of <50 copies/mL) at each time point (after 6, 12 and 24 months of follow up) will be estimated, as well as proportion of individuals with VL of <200 copies/mL. CD4 counts will also be assessed. The proportion of participants with virologic failure (2 consecutive HIV RNA VL  $\geq$ 200 copies/mL or one HIV RNA VL level  $\geq$ 200 copies/mL followed by a discontinuation of CAB+RPV LA regimen) will be estimated and time to failure will be assessed by the Kaplan-Meier method. The two-sided 95% associated confidence interval will be calculated with Kalbfleisch and Prentice's formula. Time to event will be defined as the time between the date of the initiation of CAB+RPV LA regimen and the date of virologic failure. Follow-up will be censored at the analysis time point, or the date of last study contact, or date of discontinuation of CAB+RPV LA regimen, or the date of lost to follow-up, whichever will occur first.

Genotypic resistance testing will be performed in participants with confirmed HIV RNA VL  $\geq$ 200 copies/mL. Resistance interpretation will be given using the Stanford algorithm (https://hivdb.stanford.edu/hivdb/by-mutations). All drug resistance mutations identified will be described and number and percentage indicated. The proportion of participants with genotypic resistance viruses among those with virological failure will be estimated by the number of participants with genotypic resistance viruses divided by the total number of participants with virological failure. The associated two-sided 95% exact (Clopper–Pearson) confidence intervals will be calculated. The frequency of viral subtype among those with virologic failure will be reported.

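### Section 8.4 states the resistance precision (12.7% and 21.9%) from a normal approximation, not from the exact method it declares; the exact values are 13.2% and 22.8%.

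*Protocol*

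**What the plan says.** Section 8.4 rests the study size on precision alone, with no hypothesis test. It names one method for all three precision tables: "constructed using the exact Clopper-Pearson method based on the cumulative probabilities of the binomial distribution, are presented in Table 2, 3, 4". For resistance it says "we assume a 50% resistance rate at month-24 among those with virological failure". With failure rates of 2 to 6% in 1000 participants, "the number of participants to be tested for genotypic resistance will range from 20 to 60 individuals". It then states that "the precision for the estimation of resistance rate will range from 12.7% (with 60 individuals) to 21.9% (with 20 individuals") and refers to Table 4. That table lists limits of 0.27 to 0.73 (width 0.46) at 20 individuals and 0.37 to 0.63 (width 0.26) at 60.

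For the analysis itself, section 8.7, Aim 3, says of the resistance proportion: "The associated two-sided 95% exact (Clopper–Pearson) confidence intervals will be calculated".

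As background, section 8.4 cites an earlier switch trial with virologic failure of 1.6% (95% CI 0.5 to 3.4) at week 48, described as two confirmed HIV RNA values of at least 50 copies/mL, and discontinuation of 8.4% (95% CI 5.6 to 12.1). The next sentence reads: "Among the 3 individuals with confirmed virological failure, all selected drug resistance mutations". No denominator is given.

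**The concern.** The text, the declared method and the table should give one answer for the resistance precision, and they do not. Half of Table 4's width at 20 individuals is 0.46/2 = 0.23, while the sentence that cites the table gives 0.219. Resistance appears in the study title and in objective 4, and it is the least precisely estimated of the three quantities in section 8.4. A reader who takes the text at face value gets an error bar slightly too narrow for the analysis that will be run.

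The cited failure rate is a separate, smaller matter. It stands beside a count of three cases that should belong to the same endpoint, yet the two do not agree. A reader using this paragraph to judge the assumed range of failure rates cannot tell which figure to believe.

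**Working it through.** **Inputs.** P = 0.5, n = 20 and n = 60, Clopper-Pearson as the declared method, the stated precision and the Table 4 rows (all section 8.4); Clopper-Pearson for the resistance analysis (section 8.7, Aim 3).

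**Step 1: reproduce the stated figures.** The normal-approximation (Wald) half-width is 1.96 × √(P(1−P)/n).
- n = 60: 1.96 × √(0.25/60) = 0.1265, or 12.7%.
- n = 20: 1.96 × √(0.25/20) = 0.2191, or 21.9%.

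Both match the text. The alternatives checked do not: Wilson gives 12.3% and 20.1%, and Wald with continuity correction gives 13.5% and 24.4%.

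**Step 2: apply the declared method.** For x events in n, the Clopper-Pearson limits are the 2.5% quantile of Beta(x, n−x+1) and the 97.5% quantile of Beta(x+1, n−x).
- 30/60: 0.368 to 0.632, width 0.264, half-width 0.132.
- 10/20: 0.272 to 0.728, width 0.456, half-width 0.228.

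The shortfalls are 13.2 − 12.7 = 0.5 points and 22.8 − 21.9 = 0.9 points.

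**Step 3: compare with Table 4.**

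| n | Table 4 limits | Exact limits | Wald limits |
|---|---|---|---|
| 20 | 0.27 to 0.73 | 0.272 to 0.728 | 0.281 to 0.719 |
| 30 | 0.31 to 0.69 | 0.313 to 0.687 | 0.321 to 0.679 |
| 40 | 0.34 to 0.66 | 0.338 to 0.662 | 0.345 to 0.655 |
| 50 | 0.36 to 0.64 | 0.355 to 0.645 | 0.361 to 0.639 |
| 60 | 0.37 to 0.63 | 0.368 to 0.632 | 0.373 to 0.627 |

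The limits at 20, 30 and 40 fit only the exact method. At 20 the text implies a width of 2 × 0.219 = 0.44, against 0.46 in the table. At 60 both methods round to the same limits. The only sign is the width, 0.26 in the table against 2 × 0.1265 = 0.25, and this is weak because the table's widths equal the differences of its rounded limits.

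**Step 4: check the sister sentences.** At N = 1000 the exact half-widths are 0.92 to 1.52 points for failure rates of 2 to 6%, and 1.73 to 2.32 points for discontinuation rates of 8 to 16%. The text gives 0.9 to 1.5 and 1.7 to 2.3. Only the resistance sentence departs from the declared method.

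**Step 5: the cited failure rate.**
- Three cases make 1.6% when n is near 3/0.016 = 187.5; rounding allows 182 to 193. The exact interval there is about 0.3 to between 4.5 and 4.7, not 0.5 to 3.4.
- A search over counts below 130 and n from 50 to 1499 finds no pair that gives 1.6% with a Clopper-Pearson interval of 0.5 to 3.4.
- If the companion 8.4% (5.6 to 12.1) is a Clopper-Pearson interval, only 26/308 and 26/309 match in that range of n. At 308, three cases are 0.97% (0.2 to 2.8), and 1.6% is five cases (5/308 = 1.62%, 0.5 to 3.7).
- That denominator depends on the method assumed. A Jeffreys interval gives 8.4% (5.6 to 12.1) at 24/285.

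**The case against.** The strongest reply is that the slip is trivial. It moves the stated precision by less than one point, Table 4 already has the right limits, nothing is tested, and neither the sample size nor any analysis changes. All of that is true, and it limits the weight of the point. It does not remove the point: the sentence still contradicts its own method and the table it cites.

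On the cited rate, the 1.6% and the three cases may belong to different endpoints, for example a single-time-point measure and confirmed failure. That is plausible, but the protocol labels the 1.6% as confirmed. If this is the explanation, the label is wrong, and the interval still needs checking.

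A reader might go further in several ways that the documents do not support.
- **That the 20 to 60 failures are wrong.** They are correct arithmetic: 2% and 6% of 1000, stated as a conditional range. They are not derived from the cited 1.6%.
- **That resistance precision is really about ±25 to 31 points.** This puts week-48 rates (16 or 10 failures per 1000) into a 24-month estimate. Under an assumed constant hazard, 104/48 = 2.17 times the follow-up gives 1 − 0.984^2.17 = 3.4% (34 failures) and 1 − 0.9903^2.17 = 2.1% (21 failures), both inside 20 to 60.
- **That the cited rate should be rewritten as 3/308.** The 308 is a back-calculation that assumes an interval method, and the paired failure interval does not reproduce under that method.
- **That attrition or missing genotypes make the tables too optimistic.** The documents give no such attrition figure. Resistance testing at failure is a site-selection condition. A value of at least 200 copies/mL followed by discontinuation counts as failure. In Table 3, discontinuation is the outcome itself.

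**Conclusion.** The main point stands, and it is small. The resistance precision in section 8.4 was computed by the normal approximation, whereas the section and the Aim 3 analysis specify Clopper-Pearson. The correct figures are 13.2% with 60 individuals and 22.8% with 20, so the text is optimistic by 0.5 and 0.9 points. This rests only on inputs printed in the protocol. The conflict with Table 4 is plain at 20 individuals and no more than a rounding matter at 60.

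The secondary point also stands, as an inconsistency to resolve and not as a known error in one figure. The label, the 1.6%, its interval and the three cases cannot all describe the same confirmed-failure endpoint with a Clopper-Pearson interval. Which element is wrong cannot be settled from the protocol. The reading that 1.6% is five cases and three cases are 1.0% holds only if the denominator is about 308 or 309, which is an assumption to confirm.

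Nothing here shows that 1000 participants are too few or that the range of 20 to 60 failures is mistaken.

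**What to change.** In section 8.4, replace 12.7% with 13.2% and 21.9% with 22.8%. Leave Table 4 and the sample size unchanged. The cost is a two-number edit, after which the stated precision is slightly less favourable.

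In the same section, check the cited week-48 failure result against the source. State the endpoint and its viral-load threshold, the number of cases, the denominator, the rate and the interval with its method, so that they agree with one another. If the rate and the three cases belong to different endpoints, label each one. Do not insert a back-calculated rate without that check. This costs one look-up and a sentence of text.

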#### 8.5. Data Collection

Following the approval of CAB LA and RPV LA, the study will collect follow up data prospectively on 1000 PLWH treated with the CAB+RPV LA regimen, for a follow-up period of 24 months. Participants who discontinue CAB+RPV LA regimen will be followed up for 48 months after switching to another ARV regimen. The NEAT ID Network coordinating center will receive data from the clinical sites per the protocol for the study. Detailed data collection form will be used to collect comprehensive data from clinical sites including dates of injections, clinical and laboratory parameters (virologic, immunologic, biochemistry, haematology and pathology), documented history of resistance at regimen initiation, resistance and HIV subtype data at virologic failure and after discontinuation and switching to another ARV regimen. Only clinical sites that, as SoC test all participants at virologic failure, for resistance and HIV subtype data and after discontinuation and switching to another ARV regimen will be included in the study.

In order to maintain confidentiality, the subject will be identified only by subject number. Subject data will be collected via extraction from individual medical record as source data by appropriately trained and authorised member(s) of the study team who must be identified and authorised in writing by the Principal Investigator (PI). A delegation of responsibility log will be updated accordingly.

Sites will provide / upload data every 6 months to the data management team who will store the data on a secure database with access to authorised personnel of the study management team only, maintained the log of authorised personnel by the sponsor representative.

#### 8.6. Data management

#### 8.6.1. Data handling conventions

Data will be handled in accordance with data handling guidelines provided to sites. The Study Monitor and Data Manager will review data on an on-going basis and raise any discrepancies with site staff as required. Identified only by subject number, the data are de-identified at all times.

#### 8.6.2. Timings of Assessment during follow-up

Available data will be collected from enrolled participants every 6 months and deidentified data will be reported to the data coordinating centre.

#### 8.7. Data analysis

All enrolled participants who receive at least one dose of the CAB+RPV LA regimen will be included in the analysis. Participants who are prescribed but never receive a dose of CAB+RPV LA regimen will be excluded from the analysis. Study results will be stratified by the regimen used (Q4/Monthly dosing vs Q8/Every 2 month dosing). Further, study results for co-infected patients with hepatitis B or C will be presented separately. All continuous variables will be summarized using the following descriptive statistics: n (non-missing sample size), mean, standard deviation, 1st quartile, median, 3rd quartile, maximum and minimum. The frequency and percentages (based on the non-missing sample size) of observed levels will be reported for all categorical variables. Data will be analyzed using SAS®, SPSS® or STATA®.

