#### 6. RATIONALE AND BACKGROUND

#### 6.1. Background

Cabotegravir (CAB), a human immunodeficiency virus type-1 (HIV-1) integrase strand transfer inhibitor (INSTI), in combination with Rilpivirine (RPV), an HIV-1 non-nucleoside reverse transcriptase inhibitor (NNRTI), is indicated as a complete regimen for the treatment of Human Immunodeficiency Virus type 1 (HIV-1) infection in adults who are virologically suppressed (HIV-1 RNA <50 copies/mL) on a stable antiretroviral (ARV) regimen without present or past evidence of viral resistance to, and no prior virological failure with agents of the NNRTI and INI class. Prior to the initiation of CAB long acting (LA) injection, CAB tablets together with RPV tablets should be taken for approximately one month (at least 28 days) to assess tolerability to CAB and RPV.

Treatment with CAB+RPV LA should be prescribed by a physician experienced in the management of HIV infection. Each injection should be administered by a healthcare provider (HCP). Prior to starting the regimen, the HCP should carefully select PLWH who agree to the required injection schedule and counsel individuals about the importance of adherence to scheduled dosing visits to help maintain viral suppression and reduce the risk of viral rebound and potential development of resistance associated with missed doses. Following discontinuation of CAB in combination with RPV injection, it is essential to adopt an alternative, fully suppressive ARV regimen per the summary of product characterization (SmPC).

The Marketing Authorization Holder (MAH) proposes a prospective cohort study to monitor for clinical effectiveness, discontinuation and resistance among PLWH receiving CAB+RPV LA in routine clinical practice. The proposed multi-site study "Real-world evidence for effectiveness of Two Drug Regimen, Antiretroviral therapy with integrase inhibitors plus a reverse transcriptase inhibitor Drug (COMBINE-2)" for the CAB+RPV LA regimen will be conducted through collaboration with NEAT ID Network, a well-established network of clinical sites across Europe.

The study will not require any changes to the standard of care that PLWH receive, and decisions on ARV treatment are made by the healthcare providers taking into account the treatment history, individual clinical characteristics and local guideline or recommendations. A detailed study protocol, once approved by EMA, will be implemented by the NEAT ID Network team.

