#### 8.2. Study Population and Setting

#### 8.2.1. Study Setting

Potential NEAT ID investigational sites across Europe will be contacted for feasibility and resistance testing practices as part of their SoC. Clinical sites with resistance testing following virologic failure as part of SoC and the ability to perform the tests will be selected to participate in this study. Follow-up period will start from the date of starting the treatment regimen after approval and commercial availability of the regimen.

NEAT ID Network team will perform site monitoring activities to assess protocol issues, consent, data quality and Study Management quality performance.

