#### 8.3. Variables

#### 8.3.1. Exposure definitions

All new users of CAB+RPV LA regimen treated per the approved SmPC for CAB and RPV oral and LA formulations will be included in the study. The study period will include the month-long oral lead-in, followed by injectable long acting regimen use.

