# AIM 2. Assess adherence, durability and discontinuation for PLWH starting CAB+RPV LA regimen

The proportion of study participants discontinuing the regimen will be assessed at 6, 12-and 24-months using the Kaplan-Meier method. The two-sided 95% confidence intervals of the proportions will be calculated with Kalbfleisch and Prentice's formula. Time to event will be defined as the time between the date of the initiation of CAB+RPV LA regimen and the date of discontinuation of CAB+RPV LA regimen. Death, cause of death where available and lost to follow-up will be excluded from this analysis but will be tabulated and reported separately. Follow-up will be censored at the analysis time point. The estimated median time to discontinuation will be calculated with the two-sided 95% associated confidence interval. Reasons for discontinuation will be given and frequencies and percentages will be reported. Number of individuals that experience blips  $\geq$ 50 to <200 copies/mL will be tabulated along with the number of individuals that have CVF and remain on regimen. Kaplan Meier curves will be plotted with the number of participants at risk at baseline, 6, 12, and 24-month.

The number and proportion and the two-sided 95% associated confidence interval of participants that missed one or more consecutive injections without taking daily oral bridging therapy or any other oral ARV regimen while not on CAB+RPV LA regimen will be calculated. The proportion will be estimated by the number of individuals who missed one or more consecutive injections divided by the total number of study participants in the analysis. The mean and median number of injections missed during a 12-month period will be described by median, 1st quartile, and 3rd quartile.

The number and proportion and the two-sided 95% confidence interval of proportion of individuals who received the injections seven or more days later than their scheduled

injection visit will be calculated. The proportion will be estimated by the number of individuals who received the injections seven or more days later than their scheduled injection visit divided by the total number of study participants in the analysis. The duration of delayed injections will be described by median, 1st quartile, and 3rd quartile.

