## CAB+RPV LA regimen

Lead-in Regimen			
Date lead-in regimen started	LDSTDAT		
Regimen used for lead-in	LDREG		
Did the subject adhere to the lead-in regimen?  No Yes	LDADHERE		
If no, how many days were missed	LDDYMISS		
Did the subject continue on to receive the CAB+RPV LA regimen?	○ No ○ Yes		
If no, please give reason did not continue	LDREAS		
Dosing Schedule			
Date  DSTYPE  Reason branchinging therapy  Did the sub-	Change in Dosing Schedule Type?  Schedule Type?  Schedule  DSTYPEREAS  PV LA regimen	Was the injection given?  DGIVEN  Actual Injection Date  DACTDAT	Did the subject take oral bridging therapy or any other oral ARV regimen?  DBRID

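### Participants who stop during the oral lead-in fall outside the objective 2 discontinuation rate and no stated output reports them; regimen initiation is not tied to lead-in start or first injection

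*Protocol*

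**What the plan says.** The analysis set is fixed in Section 8.7: "All enrolled participants who receive at least one dose of the CAB+RPV LA regimen will be included in the analysis". The next sentence gives the complement: "Participants who are prescribed but never receive a dose of CAB+RPV LA regimen will be excluded from the analysis".

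Section 8.3.1 describes the observed period: "The study period will include the month-long oral lead-in, followed by injectable long acting regimen use". Section 6.1 gives the purpose of the lead-in tablets, which "should be taken for approximately one month (at least 28 days) to assess tolerability to CAB and RPV".

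In Annex 1, the form headed CAB+RPV LA regimen opens with a lead-in block: start date (LDSTDAT), adherence, and then the question "Did the subject continue on to receive the CAB+RPV LA regimen" (LDCONT), with a free-text reason if the answer is no (LDREAS). The Regimen Initiation form holds a separate regimen start date (LASTDAT) without a definition.

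The clock for discontinuation is set under Aim 2 of Section 8.7: "Time to event will be defined as the time between the date of the initiation of CAB+RPV LA regimen" and the date the regimen is stopped. Section 8.2.1 says: "Follow-up period will start from the date of starting the treatment regimen". Neither place says whether that date is the first lead-in tablet or the first injection. Under Aim 2, only deaths and losses to follow-up are set aside for separate tabulation.

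**The concern.** Objective 2 concerns adherence, durability and discontinuation among people starting the regimen. The analysis set depends on something that happens after enrolment, namely reaching a dose of the long-acting regimen. The people removed by that rule have, by definition, stopped early, and they stopped in the phase whose stated purpose is to test tolerability. A rate computed without them describes the injected subset, and a reader of the report would have no figure from which to recover the rate among all starters.

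The undefined start date adds a second problem. Two analysts could build different curves from the same data, one with the clock at LDSTDAT and one with it at first injection, with the 6-, 12- and 24-month estimates about a month apart.

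**Working it through.** **Step 1. The plan's own figure.** Section 8.4, Table 3, gives exact Clopper-Pearson 95% limits for the discontinuation rate with N = 1000. Recomputing from beta quantiles gives 6.39-9.86% at 8%, 8.21-12.03% at 10%, 10.05-14.18% at 12%, 11.91-16.31% at 14% and 13.78-18.42% at 16%. All five rows agree with the printed limits after rounding. The precision figures are right; the question is who is counted.

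**Step 2. Who is counted.** Take a participant who enrols, starts the lead-in and stops before any injection.
- Section 8.3.1: inside the study period.
- Annex 1: recorded, with LDCONT = No and a reason in LDREAS.
- Section 8.7: the form asks whether the person went on to receive the long-acting regimen, so a No means no dose of it, and the person is excluded.
- Aim 2 text: not among the groups tabulated separately.

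**Step 3. Size of the exclusion.** Let q be the share of starters who stop in the lead-in (not in the documents; assumed 1-3%) and p the rate among those injected. The rate among all starters is q + (1 - q)p = 1 - (1 - q)(1 - p).

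| q (assumed) | p = 8% | p = 16% |
|---|---|---|
| 1% | 1 - 0.99 × 0.92 = 8.9% | 1 - 0.99 × 0.84 = 16.8% |
| 2% | 1 - 0.98 × 0.92 = 9.8% | 1 - 0.98 × 0.84 = 17.7% |
| 3% | 1 - 0.97 × 0.92 = 10.8% | 1 - 0.97 × 0.84 = 18.5% |

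The shift is 0.8 to 2.8 points, against a planned half-width of 1.7 to 2.3 points.

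**Step 4. When it passes the planned interval.** Solve q + (1 - q)p = U, where U is the upper limit in Table 3, so q = (U - p)/(1 - p).
- p = 8%, U = 9.9%: q = 0.019/0.92 = 2.1%.
- p = 16%, U = 18.4%: q = 0.024/0.84 = 2.9%.

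**Step 5. The start date.** Suppose the clock began at lead-in start while inclusion required an injection. No analysed person could then discontinue in the first month. As an illustration, assume a constant hazard matching 8.4% in 12 months (the figure Section 8.4 cites for week 48, treated here as a year): h = -ln(1 - 0.084)/12 = 0.0073 per month. Compare 1 - exp(-hm) with 1 - exp(-h(m - 1)).

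| m (months) | Full exposure | First month event-free |
|---|---|---|
| 6 | 4.3% | 3.6% |
| 12 | 8.4% | 7.7% |
| 24 | 16.1% | 15.5% |

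This applies only under that mixed reading. If inclusion and the clock both start at the first injection, there is no such month.

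**The case against.** The strongest reply is that Sections 8.7 and Aim 2 use the same term for the regimen, so it should be read the same way in both.
- If the regimen includes its oral phase, a lead-in tablet is a dose, lead-in stoppers stay in, and nothing is lost. Section 8.3.1 gives this some support by defining new users through both oral and long-acting formulations, and the lead-in block sits on a form named after the regimen.
- If the regimen means injections, initiation is the first injection and there is no event-free month. People who never received it did not start it, so leaving them out matches the stated target. Discontinuation among those actually treated is a legitimate quantity.

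Two further points are fair. Lead-in stops are collected, so they are not lost. For virologic outcomes, the window of ±6 weeks under Aim 3 is wider than a one-month change of origin.

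Much of this stands. A reader might infer that the plan builds in immortal time. The documents do not support that, because it requires reading dose as an injection in one place and initiation as lead-in start in another. A reader might also infer that Section 8.3.1 contradicts Section 8.7. It does not: collecting lead-in data is compatible with starting a curve at first injection, so this is a mismatch between the observed and the analysed period.

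The first branch is harder to sustain. The form asks, after the lead-in, whether the participant went on to receive the regimen, which makes little sense if the lead-in tablets already count as a dose of it. The second branch leaves the reporting gap in place. Nor is this only detail that a statistical analysis plan may supply, since the exclusion rule itself is stated in the protocol.

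**Conclusion.** The point holds in a limited form. On the most natural reading, the stated exclusion removes lead-in stoppers from the objective 2 rate, no stated output reports them, and the start date is left open. It does not show immortal-time bias or an internal contradiction.

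The direction is certain: counting lead-in stops can only raise the rate among starters. The size is not, because q is assumed. At 1-2% the all-starter rate stays inside the Table 3 upper limits; at about 2.1% (for 8%) to 2.9% (for 16%) it passes them. Table 3 attaches no time point to its 8-16% range, so these figures should not be read as 24-month rates. The calculation also ignores the one-month difference between the two time origins. This is an inexpensive improvement to the plan and does not call the on-injection analysis into question.

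**What to change.** 1. In Section 8.7, state that the qualifying dose and the initiation date both mean the first long-acting injection for the on-injection Kaplan-Meier analyses. Align Sections 8.2.1 and 8.3.1, and define LASTDAT to match.
2. Among all enrolled participants who started the lead-in, report the number and proportion not continuing to injections, with reasons (LDCONT, LDREAS).
3. Add one supplementary discontinuation curve from lead-in start (LDSTDAT) that counts lead-in stops as events.

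Two practical notes. LDREAS is free text, so the reasons need coding, for instance to the Table 1 list in Section 8.3.2. The lead-in block has no stop date of its own, so sites should be told to enter it in the discontinuation date on the same form (DISCONDAT). An imprecise date within the lead-in month would not change the 6-, 12- or 24-month estimates.

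The cost is a few sentences, one table and one curve, with no new visits or tests. The all-starter figure will be slightly less favourable than the on-injection one.
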